Trauma Informed Guilt Reduction Therapy

NCT02512445

Original Document Date: November 14, 2024

8. Aims and Objectives

Primary Aim: To evaluate the efficacy of TrIGR for reducing deployment-related guilt in Veterans of OEF/OIF/OND.

Hypothesis 1: Veterans in TrIGR compared to Veterans in supportive care therapy (SCT), will have significantly greater reductions in deployment-related guilt severity at the end of treatment and post-treatment follow-up.

Secondary Aims: To examine whether TrIGR reduces distress and shame and improves quality of life. We are also interested in the degree to which gains are maintained during the follow up periods.

Hypothesis 2: Veterans in TrIGR, compared to Veterans in SCT, will have significantly greater reductions in distress, shame, guilt cognitions, avoidant coping, and significantly more improvement in their quality of life at the end of treatment and at post-treatment follow-up.

Hypothesis 3: Per the NAG model, guilt cognitions, distress and avoidant coping will partially mediate the treatment effect on guilt severity.

Exploratory Aim: By including Veterans with a variety of deployment-related presenting problems, we will be able to conduct exploratory analyses that will inform future research regarding for whom and under what conditions TrIGR is most effective.

Objective 1: To explore relationships between TrIGR effects and PTSD and depression symptom severity, suicidal ideation (SI) and alcohol/substance use.

Objective 2: To explore whether reductions in guilt, shame, and avoidant coping will partially mediate the treatment effect on PTSD symptoms among **Veterans with a PTSD diagnosis** and/or depression symptoms among **Veterans with a depressive disorder**.

9. Approach

9.1. Design. This prospective, randomized, controlled trial will assess the efficacy of TrIGR as compared to SCT for the treatment of male and female Veterans with guilt related to a traumatic event that occurred during deployment. 150 participants will be enrolled through the San Diego and Providence VAs and randomized at the individual level. All eligible participants will complete an in-person baseline assessment, receive 6 sessions of TrIGR or SCT in individual format, complete weekly measures related to the primary and secondary aims, and complete a follow-up assessment immediately post-treatment, and 3- and 6-months later.

9.2. Timeline. We propose a study lasting 4 years including:

Phase I Set up (months 0 - 5): Start-up activities will include finalizing approvals, hiring and training of the research staff and therapists providing the study interventions, and setting up data entry and management procedures in collaboration with study statistician, [name]. Patient recruitment protocols will be developed, tested, and revised.

Phase II RCT (months 6 - 42): Participant recruitment and enrollment will occur in months 6 to 34, with the intervention period occurring from months 6 to 36. Assessment will continue for an additional six months past the end of the intervention period (to month 42) to complete the final follow-up assessments. Methods and procedures are consistent with CONSORT guidelines for conducting and reporting RCT's [49]. We expect to recruit 2-3 participants per site per month, which will allow us to meet our recruitment target of 150. Data entry and management will begin with preliminary statistical analyses in the second year and will continue through the end of the study.

Phase III Dissemination (months 43 - 48): The final six months will be used for data analysis and dissemination of results via conferences and in manuscripts.

9.3. Procedures. Eligible Veterans will be recruited from two VA Medical Center sites, one in San Diego, CA, and one in Providence, RI. Potential participants will be receiving or presenting to care at VA enrollment, primary care, mental health, MST, or other VA services and will be referred by clinicians or staff in those clinics (see letters in Support 2e - 2g). Veterans may also self-refer to the study in response to advertising materials that will be distributed in patient areas and in the community. All potential participants will undergo a brief (15 minute) screen (following informed consent to be screened) conducted by the site project coordinator to determine preliminary eligibility. Veterans who meet the screening requirements will complete consenting procedures and will be invited for a full baseline assessment. Participants who meet inclusion/exclusion criteria as confirmed by the baseline assessment will be randomized to TrIGR or SCT. All participants will be assessed at baseline, immediately post-treatment, and at 3- and 6-month post-treatment follow-ups. Participants will be compensated for completing each of the four assessments with \$40 per assessment. We anticipate that baseline assessments will take approximately 3 hours and follow-ups will take approximately 2 hours. Participants will also complete brief weekly self-report assessments (15 minutes) during treatment. We will attempt to obtain follow-up data on all participants, regardless of whether they complete the intervention.

9.4. Participants: Inclusion/Exclusion Criteria, and Rationale. Participants will be male and female OEF/OIF/OND Veterans, at least 18 years of age, who endorse distress from guilt related to an event or events that occurred during a military deployment. Women and members of diverse ethnic and racial groups will be recruited for this project. Eligibility criteria were designed to recruit a heterogeneous and representative sample of Veterans with guilt and distress related to trauma that occurred on deployment. Eligibility criteria are broad in order to capture the many manifestations of distress related to guilt among Veterans.

Inclusion criteria: (1) having been deployed during Operation Enduring Freedom (OEF), Operation Iraqi Freedom (OIF), or Operation New Dawn (OND); (2) a score of 3 or higher ("very true" or "extremely true") on feeling posttraumatic guilt much or all of the time and scoring 3 or higher ("very true" or "extremely true") on at least one guilt cognition factor (hindsight bias/responsibility, wrongdoing, or lack of justification) on the Trauma Related Guilt Inventory [TRGI; 18]; (3) distress as indicated by an initial [BSI-18; 50] score over 63 and a Clinical Global Impressions Severity Scale [CGI-S; 51] rating of at least markedly ill; (4) not currently receiving trauma-focused treatment such as PE or CPT (those currently in treatment may qualify following completion); (5) English literacy; (6) intention to stay in Providence or San Diego area during study participation; (7) willingness to attend psychotherapy and assessment sessions; and (8) if meeting diagnostic criteria for mild or moderate AUD/SUD, willingness to set goals to reduce alcohol and/or substance use during the treatment period [52].

Exclusion criteria: Moderate or severe cognitive impairment on the Brief Neuropsychological (NP) Assessment Battery [53] as this may interfere with ability to benefit from treatment. Acutely suicidal individuals (assessed using the suicide items from the depression measures described below) will be referred for more appropriate treatment (see Human Subjects section). Current severe AUD/SUD (in the past two months) based on DSM-5 criteria will be excluded as these Veterans may require a higher level of care. Current psychosis or mania independent of substance use will be excluded because the presence of these disorders can impede therapy progress. Veterans residing more than 50 miles from their nearest study site, with life threatening or unstable medical illness, or inability to read will be excluded.

Who will not be excluded: Veterans with mild cognitive impairment, mild to moderate alcohol and substance use disorders, suicidal ideation without acute suicidality, and anxiety and depressive disorders will not be excluded because of their high co-occurrence with traumatic guilt [13-17] and recent findings that individuals with mild to moderate TBI can benefit from cognitive behavioral treatments [54]. We elected to allow Veterans to continue to engage in TAU other than trauma-focused treatments, as we do not expect TrIGR to be a stand-alone treatment for disorder specific conditions. Accordingly, all participants will be encouraged to continue to receive AUD/SUD and mental health treatment as needed, including pharmacotherapy, with their current providers throughout the study. TAU in both San Diego and Providence VAMCs consists of outpatient treatment for SUDs including relapse prevention using a

cognitive behavioral model, complementary groups such as relaxation training, sleep hygiene, and smoking cessation. Additionally, Veterans may be engaged in psycho-educational groups about PTSD (e.g., PTSD 101) that do not include trauma processing. Participants will be asked not to take part in any trauma-focused treatment such as PE, CPT, or Eye Movement Desensitization and Reprocessing (EMDR) during study participation. We will carefully track all treatment received during the active treatment and follow-up phases of the study and will evaluate whether differences in TAU are roughly equivalent across treatment groups and sites. If differences across sites exist, site will be included as a fixed effect in our analyses.

9.5.1. Recruitment. We will use a multi-pronged recruitment strategy to obtain an intake rate of approximately 2-3 participants per month per site during the study. Veterans can contact our study in response to (1) a referral from staff or providers in mental health, primary care, MST, and substance use treatment programs; and (2) advertisements in print and web-based media posted throughout the study sites. Additionally, Veterans newly referred for mental health treatment first attend an orientation group or an initial mental health assessment where the services provided in the program are explained. Providers will describe this study as one of the options for Veterans who they deem to be potentially appropriate. The Project Coordinator at each site will also attend the orientation groups to present information about the study. Interested Veterans will complete a “Consent to Contact” form that gives research staff permission to contact the Veteran to further explain the study and conduct an initial screening. Potential participants who contact us by telephone will first provide verbal consent and undergo the initial screening over the telephone.

Whether by telephone or in person, the screening takes approximately 15 minutes to complete and is intended to identify guilt and distress related to a traumatic event that occurred during deployment. For those who screen positive, an appointment will be made for written informed consent and a full baseline assessment. Similarly, the primary methods of recruitment for existing mental health patients will be through provider referral or self-referral. Provider referral has proven successful for recruitment in our previous trials. The study team will reach out to relevant mental health providers at each site on a regular basis (e.g., by presenting in clinic meetings and/or targeted emails) to educate providers about the study and maintain their awareness of the opportunity. Providers will share information about the study and request permission for the study team to contact potentially eligible patients. If a Veteran is interested in participating in the study, he/she will be contacted by study staff and complete the telephone screening as described above. Alternatively, Veterans may self-refer to the study based on advertisements or word of mouth.

9.5.2. Randomization. [name] will prepare the randomization table prior to the start of recruitment for each site. Randomization will be conducted separately at each site. We will use a permuted block randomization system, in which treatment assignment order is random within each block, with an equal number of participants assigned to each treatment. Block sizes will vary in random sequence between 2 and 4. We will stratify randomization by gender. We will evaluate successful randomization of other factors, such as symptom and substance use severity and demographics, and control for these factors if needed as described in section 9.11.2.

9.5.3. Feasibility of recruitment. VASDHS will serve as one of the two recruitment sites for the proposed research. We expect that three clinics within mental health services from which we will recruit heavily will be the PTSD treatment program, the Substance Abuse Mental Illness (SAMI) program, and the MST clinic. The PTSD clinic (which [name] formerly directed) completes over 50 new intakes with OEF/OIF/OND Veterans each month. During Q4 of FY2014, 540 OEF/OIF/OND Veterans with a PTSD diagnosis were seen for mental health services (either three or more sessions of psychotherapy or one medication appointment). The SAMI program has 34 OEF/OIF/OND Veterans enrolled in in the past three months. The program completes approximately 8 new intakes with OEF/OIF/OND Veterans each month. The MST Clinic sees approximately 18 new Veterans and 60 ongoing Veterans per month who are OEF/OIF/OND. We will have access to eligible participants based on the relationships and approvals we have already secured as part of Drs. [name] and [name]’s ongoing research programs and through their roles in the PTSD and substance use treatment programs at the San Diego VA. [name] current VA-

funded RCT is recruiting a similar population (although not limited to OEF/OIF/OND Veterans) and has been recruiting an average of 4-5 Veterans per month, 42% of whom (n = 33) are OEF/OIF/OND. Recruitment in the current RCT will be coming to completion as recruitment for the proposed study would be beginning, thus we will continue to receive a steady flow of referrals to our program of research.

Within VASDHS, we assessed feasibility of recruitment for the proposed study in regard to the inclusion criteria of having guilt related to trauma and having served in OEF/OIF/OND, neither of which are required in our current studies. Specifically, we examined what percent of participants enrolled in [name] current studies during the past year would meet the criteria regarding trauma related guilt using the Trauma Related Guilt Inventory (TRGI) and having served in OEF/OIF/OND. 27% (n = 84) of Veterans initiating outpatient PTSD treatment and 36% (n = 13) of PTSD/AUD Veterans enrolling in [name] current RCT met the OEF/OIF/OND and TRGI guilt criteria described in section 9.4 under Inclusion Criteria. We will have 28 months of active recruitment, and thus need to recruit 2-3 Veterans per month per site to reach our target of 75 at the San Diego site. Given recruitment rates in our current projects (4-5 per month), the high rates of guilt endorsed by our current OEF/OIF/OND participants, and the fact that neither AUD nor PTSD diagnosis is required for the proposed study, **our recruitment target is highly feasible.**

The Providence VA Medical Center (PVAMC) is the other site for the proposed research. The PVAMC is a 120 bed general medical facility that provides acute inpatient and outpatient care to the Veteran population throughout Rhode Island and Southeastern Massachusetts. During Fiscal Year 2014, over 2200 OEF/OIF/OND Veterans sought mental health treatment in the outpatient PTSD, General Mental Health, Returning Veterans, and Substance Abuse Treatment Program clinics. These numbers are more than sufficient to meet our recruitment goals of 2-3 Veterans per month for a total of 75 OEF/OIF/OND Veterans with deployment-related guilt and distress.

9.5.4. Attrition. Based on attrition rates in comparable research studies of exposure-based treatment for trauma related distress and our own preliminary work, we conservatively estimate that approximately up to 20% of participants will be lost to measurement follow-up prior to the final (6-month post-treatment) assessment [55]. Completion of TrIGR is defined *a priori* as attending 75% or more of the planned treatment sessions (see section 9.11.1. regarding the data analysis plan, including the plan for handling missing data and attrition).

9.5.5. Patient Retention Methods. The investigators have extensive experience in maintaining study cohorts over substantial periods of time. For example, in [name] current VA RCT, drop out has been 15% of 60 participants randomized to one of two psychotherapies for concurrent treatment of AUD and PTSD. Based on other studies with similar populations [56], we have estimated our dropout rate prior to the final assessment to be 20%. The following steps will be taken to insure high retention: (1) at all assessment points, participants will be asked to provide contact information for at least two close friends or relatives and permission to contact them; (2) a database accessible only to study staff will be maintained as a participant tracking system; and (3) computer public search engines (e.g., Accurint) will be used to locate those lost to follow-up. Prior research has given some indication of reasons why individuals may drop out of treatment [57]. We address these barriers by offering therapy at a centrally located site that is accessible by public transportation and offers free parking, by offering transportation reimbursement, and by offering therapy in individual format during daytime and early evening hours. We will encourage all participants to have a case manager through the VA so that case management issues are addressed in both treatment modalities.

9.5.6. Women and Minorities. Women comprise 11% (e.g., SAMI clinic) to 60% (Military Sexual Trauma clinic) of the Veterans seen in the clinics from which we will be recruiting and approximately 24% of Veterans in the program are minorities. Consistent with these demographics as a whole, 11% of participants in our integrated PTSD/AUD intervention studies have been women. Based on the 2010 US Census figures and consistent with our other research, we anticipate enrolling the following ethnic minority breakdowns in San Diego: Hispanic/Latino (32%), Other (including mixed race; 19%), Asian (11%), African American (5%), and Native American/Alaskan/Pacific Islander (1%). Given that this study will include recruitment from the Military Sexual Trauma Clinic, the increasing numbers of women in the

military, and increasing Hispanic proportion of the population in southern California, we will continue attempts to oversample these groups to obtain adequate recruitment of females and minorities to examine effect sizes for these groups relative to male and Caucasian counterparts.

9.6. Compensation. Participants will be compensated up to \$160 for their time and effort for completing assessments: \$40 each for baseline, post-treatment, and for the 3- and 6-month post-treatment follow-ups.

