9.8. Research Assessments

9.8.1. Outcomes. The primary efficacy outcomes of interest are reduction in the severity of guilt related to a deployment trauma at post-treatment and follow-up. We will also examine distress, shame,

quality of life, PTSD symptoms, depression symptoms, alcohol and substance use, suicidality, and potential mediators and moderators including avoidant coping, guilt cognitions, treatment process variables (e.g., attendance, homework completion), gender, and cognitive performance. All measures can be found under Support Documents.

Primary Outcome. Trauma Related Guilt Inventory [TRGI; 18] is a 32-item validated self-report measure assessing traumatic guilt. The TRGI has three scales – Guilt Severity, Distress, and Guilt Cognitions. We will use the TRGI as one of our eligibility criteria (see inclusion criteria, section 9.4) and to monitor changes in guilt and related cognitions over time. Guilt severity will be the primary outcome of interest. It is computed by adding items regarding guilt frequency and guilt intensity. Changes in guilt cognitions will be examined as a partial mediator of treatment outcomes. Internal consistency is high for the TRGI (guilt severity = .90, distress = .86, guilt cognitions = .86).

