In the second stage, we will perform sensitivity analyses for the impact that potentially informative missing data may have on the analyses. The selected method of data analysis is robust with respect to drop-out and missing data, unless the drop-out mechanism or cause of missing is informative. We will use pattern-mixture models to assess if there is bias due to drop out or missing data. These mixed models allow us to assess whether important estimates are dependent on missing data patterns, and provide overall estimates of effects by averaging over the various missing-data patterns [80]. In addition, we will consider the extension of the Pattern-Mixture models [81], which includes the incorporation of random effects in the Pattern mixture model, which allow subject-to-subject heterogeneity. All hypothesis tests will be intent-to-treat, using SPSS version 21, and will be two-sided at the .05 level where applicable. We will adjust p-values for multiple testing within each hypothesis separately by using a Bonferroni correction whenever more than one variable is being tested.

Type I error will be controlled through the following steps. The data analysis method we selected reduces the number of dependent variables drastically. We have restricted potential predictors to those with strong evidence and/or strong rationale for having an effect on the dependent variable, and in most cases we have further restricted potential predictors to one representative of each. Also, an adjusted significance level (.01 rather than .05) will be used if applicable.

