Hypothesis 3: Per the NAG model, guilt cognitions (TRGI Cognitions Scale), distress (BSI-18) and avoidant coping (COPE) will partially mediate the treatment effect on guilt severity (TRGI). For this hypothesis, we will use the same mixed effect model procedure identified in hypothesis 1. We will utilize the analytic strategy described by [85] [86] to test the mediation effect. Based on this strategy, four conditions must be met: (1) a significant relationship between the independent variable (i.e., intervention

condition) and the dependent variable, (2) a significant relationship between the independent variable and the proposed mediator, (3) a significant relationship between the mediator and the outcome, and (4) the relationship between the independent variable (intervention) and outcome must be significantly lower after controlling for the proposed mediator. To test for significant mediation, we will conduct a Sobel test. We will also use the formula provided by [87] to determine the percentage of the intervention condition to primary outcome path that was accounted for by change in our mediator [88].

Exploratory Analyses. The first exploratory objective, whether TrIGR, as compared to SCT, is associated with greater decreases in PTSD and depression symptom severity, greater reductions in suicidal ideation (SI) and greater reductions in alcohol/substance use, will be explored using mixed effect method as explained for hypothesis 1. The second and third objectives—whether reductions in guilt, shame, and avoidant coping will partially mediate the treatment effect on PTSD symptoms among Veterans with a PTSD diagnosis and among Veterans with a depressive disorder—will be explore using analytic strategy as described for hypothesis 3 [85].

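### Hypothesis 3 states partial mediation, but the planned rule shows only whether an indirect effect exists and cannot separate partial from complete mediation

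*Combined protocol and SAP*

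**What the plan says.** Section 8, Hypothesis 3, predicts that "guilt cognitions, distress and avoidant coping will partially mediate the treatment effect on guilt severity", and section 9.11.2 repeats the prediction. Section 9.8.1, under the primary outcome, says: "Changes in guilt cognitions will be examined as a partial mediator of treatment outcomes". Exploratory Objective 2 uses the same adverb for PTSD and depression symptoms, and section 9.11.2 sends it to the same analysis.

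For the test, section 9.11.2 says that "four conditions must be met". In short: (1) treatment is related to outcome; (2) treatment is related to mediator; (3) mediator is related to outcome; and (4) "the relationship between the independent variable (intervention) and outcome must be significantly lower after controlling for the proposed mediator". It adds "To test for significant mediation, we will conduct a Sobel test", and a formula from a cited source to "determine the percentage of the intervention condition to primary outcome path that was accounted for by change in our mediator".

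Section 9.11.1 sets the level: tests "will be two-sided at the .05 level where applicable", with a Bonferroni correction within each hypothesis. The power paragraph claims 80% power for Hypothesis 3 to detect a mediated effect. No section gives a test or interval for the adjusted treatment effect, an interval for the percentage, or a result that would distinguish partial from complete mediation.

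**The concern.** The hypothesis and its test do not match. Conditions 1 to 3 do not look at the remaining direct effect. Condition 4 asks only that the treatment coefficient fall, and a fall to zero satisfies it as well as a fall by half. The Sobel test asks only whether the indirect effect differs from zero. The one planned quantity that speaks to partial versus complete is the percentage mediated, which is a ratio of two estimates and has no stated uncertainty.

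What is at stake is how the model of guilt that motivates the trial is read: whether TrIGR acts only through guilt cognitions, distress and avoidant coping, or also by another route, such as the values work in Modules 3 and 4 (section 9.7.1).

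**Working it through.** **1. The plan's own figure.** The power paragraph gives 80% for the Sobel test and 0.39 as a medium path. It does not fix the treatment coding, the number analysed or the alpha for Hypothesis 3, so the 80% can only be bracketed. With both paths 0.39, residual SD 1 and treatment scaled to unit variance, SE(ab) = 0.39 × √(2/N):

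- N = 150: SE = 0.0450, z = 0.1521/0.0450 = 3.38, power = Φ(3.38 − 1.96) = 0.92 (simulated 0.99).
- N = 120: z = 3.02, power 0.86 (simulated 0.94). At alpha 0.05/3, 0.74 (simulated 0.81).
- With 0/1 treatment coding, simulated power at alpha 0.05 is about 0.56 at N = 150 and 0.43 at N = 120.

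So 80% is attainable under one coding. It is power to detect an indirect effect, not to separate partial from complete mediation, and the point does not depend on it.

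**2. Simulation inputs.** From the plan: 150 randomised 1:1; up to 20% attrition, leaving 120; total effect 0.5 SD; two-sided 0.05. Assumed, because the plan gives no values: treatment effect on the mediator a = 0.8 SD (0.5 SD as a second value), within-arm SD of 1 for mediator and outcome, one mediator, one outcome time, least squares. Rule: conditions 1 to 3 each at p < 0.05, plus Sobel at 0.05 or 0.05/3, which also stands for condition 4 because the drop in the treatment coefficient equals ab. Percentage mediated = ab / total effect.

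**3. Complete mediation** (a = 0.8, b = 0.625, ab = 0.5, direct effect 0; 6,000 trials, N = 120):

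- The rule is met in 77–78% of trials (about 86% at N = 150).
- This is almost the power of condition 1 alone: a 0.5 SD difference has power 0.78 at 60 per arm and 0.86 at 75 per arm. A zero direct effect costs nothing.
- Among trials meeting the rule, the middle 95% of the percentage is 55% to 148%. A run of 4,000 trials gave 56% to 146%, median 92%.

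**4. Less than complete mediation** (N = 120, Sobel at 0.05, 4,000 trials):

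| True share | a | Rule met | Middle 95% of percentage |
|---|---|---|---|
| 50% | 0.5 | 64% | 26% to 89% |
| 50% | 0.8 | 69% | 24% to 90% |
| 75% | 0.8 | 77% | 37% to 117% |
| 100% | 0.8 | 78% | 56% to 146% |

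The ranges overlap widely, so a point percentage cannot tell these truths apart.

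**5. Precision of the direct effect.** SE = √(1 − b²) × √(4/N) × √(1 + a²/4).

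- a = 0.8, b = 0.625: 0.781 × 0.183 × 1.077 = 0.154, a 95% half-width of 0.30 SD.
- a = 0.5, b = 0.5: 0.866 × 0.183 × 1.031 = 0.163, a half-width of 0.32 SD.

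Both are large against a total effect of 0.5 SD.

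**6. Would requiring a significant direct effect work?** With half the effect mediated, N = 120 and Sobel at 0.05, the direct effect is significant in 39% (a = 0.5) or 29% (a = 0.8) of trials meeting the rule. Over all trials that is 0.640 × 0.390 = 25% or 0.692 × 0.293 = 20%. With Sobel at 0.05/3 and a = 0.5 it is about 17%. At N = 150 (Sobel at 0.05) it is 34% or 27%. The label would be withheld in most trials where it is true.

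**7. One mediator or three.** Suppose three mediators carry the whole effect, each with a = 0.5 and b = 1/3 (assumed): total = 3 × 0.5 × 1/3 = 0.5, true direct effect 0. Adjusting for one alone leaves 0.5 − 0.5 × 1/3 = 0.33 SD if they are uncorrelated. If they correlate 0.5, the single-mediator slope is (1/3)(1 + 0.5 + 0.5) = 2/3, leaving 0.5 − 0.5 × 2/3 = 0.17 SD. Adjusting for all three leaves 0.

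**The case against.** Much can be said for the plan. Condition 4 requires the adjusted treatment effect to be estimated, and the complement of the percentage mediated is the share that remains, so the direct effect is not ignored. The strategy and the percentage formula are delegated to cited sources, which may give a criterion or a standard error; that could not be checked. With three named mediators, *partially* is also a natural description of each one taken singly, as step 7 shows. Objective 2 and section 9.8.1 speak of exploring and examining, not of confirming. The simulation is simpler than the planned longitudinal mixed model.

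These points limit the concern but do not remove it. An estimate with a half-width near 0.30 SD says little without its interval, and the plan commits to none. The mismatch between hypothesis and rule follows from the wording of the four conditions and does not need the simulated rates.

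A reader might go further and infer that Hypothesis 3 can be neither supported nor refuted. The documents do not support that: failing any of the four conditions leaves it unsupported, and in the simulated settings with half or all of the effect mediated the rule failed in 22% to 51% of trials at N = 120. A reader might also infer that the trial will report partial mediation whenever it finds any. No section contains a labelling rule, so that would be a prediction and not part of the plan.

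**Conclusion.** The point holds as a mismatch between a hypothesis and its decision rule. Hypothesis 3, Objective 2 and section 9.8.1 describe partial mediation; the rule shows whether an indirect effect exists and is met equally well when no direct effect is left. Under the stated assumptions, complete mediation passes in about 77–78% of trials at N = 120, with a point percentage anywhere from about 55% to 148%. These rates are illustrative, because the path sizes are assumed and the model has one mediator and one time point. It would be wrong to extend the point to the main result: Hypothesis 3 is secondary, and the test of Hypothesis 1 and its sample size are unaffected.

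**What to change.** - Delete *partially* (and *partial* in section 9.8.1) from the tested claim in Hypothesis 3, Objective 2 and section 9.8.1, and state the test as whether an indirect effect exists.
- Report the indirect effect, the remaining direct effect and the percentage mediated, each with a bootstrap 95% interval.
- State that complete mediation will not be inferred from a non-significant direct effect.
- Do not make a significant direct effect a condition for the label, for the reason in step 6.
- To ask whether any effect remains outside the three named mediators, estimate the direct effect with all three in one model. A single-mediator direct effect can simply be the other two.

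The cost is SAP wording and some added analysis on data already to be collected. The intervals will be wide and will make the mediation claim less definite.
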